3. STUDY DESIGN

The study will be a multicenter, randomized, double-blind trial to evaluate the efficacy of NTZ compared to placebo in treating colds due to EV/RV infection.

Subjects will be randomized 1:1 to one of the following groups:

- Group 1 (NTZ): Two NTZ 300 mg tablets b.i.d. for 5 days
- Group 2 (Placebo): Two placebo tablets b.i.d. for 5 days

Enrollment and the primary efficacy analysis will be stratified by (1) time from onset of illness to study enrollment (0-24, >24-≤36, or >36 hours from onset), (2) pre-enrollment use of symptom relief medication, and (3) presence of underlying lung condition including asthma, COPD, or past or present history of smoking.

This study is expected to run from August 2018 through April 2019.

Rationale for important issues in the study design is described below:

- *Choice of NTZ dose and duration of treatment.* The dose of NTZ used for this clinical trial (600 mg b.i.d. for 5 days) was associated with a reduction of the duration of symptoms and time to ability to perform all normal activities in subjects with EV/RV infection in a previous trial of NTZ for the treatment of influenza (Study RM08-3002). In clinical trials involving 2,886 subjects, adverse events reported by subjects receiving 600 mg NTZ b.i.d. for 5 days were similar to those of subjects receiving the placebo, with the exception of a higher rate of diarrhea (8.1% compared to 5.8% for the placebo). Studies of NTZ at higher doses have shown dose-dependent increases in the frequency of reported diarrhea and other gastrointestinal side effects, therefore no higher dose is planned for this study.
- *Choice of control groups.* A placebo control is appropriate for the study due to lack of any approved active control.
- *Choice of patient population.* The population to be studied includes adults and adolescents at least 12 years of age with EV/RV infection. This is a population similar to those selected for studies RM08-3001, RM08-3002, RM08-3003 and RM08-3004 of the NTZ 300 mg extended release tablets in more than 3,000 subjects with influenza-like illness. No safety concerns have been identified from these clinical trials.

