5.2. Baseline (day 1, same day as screening evaluation)

At baseline, the following procedures will be carried out:

1. Collection of two nasopharyngeal swabs (one from each nostril) using nylon flocked dry swabs (Copan Diagnostics) for RT-PCR and culture.
2. Collection of blood sample for laboratory safety tests.
3. Collection of a urine sample for routine urinalysis (glucose, protein and blood).
4. Review and recording of any concomitant medications.
5. Provision of an electronic diary to subject via his/her own smartphone or a provisioned device, and subject completion of baseline electronic diary under supervision and instruction of study site personnel, including the Practice Diary, FLU-PRO Questionnaire, Activity Diary, and Study Drug Intake and Temperature Diary.
6. Randomization and dispensing of study medication (medication assigned in sequential order).

7. Administration of the first dose of study medication with food (< 1 hour after food intake) under observation of Investigator or a member of Investigator's staff, and entry in Study Drug Intake and Temperature Diary.
8. Instruct subject regarding:
 - a. *Administration of study medication.* Subjects will be instructed to take the study medication (two tablets) twice daily with food (< 1 hour after food intake, preferably a high-fat meal but at a minimum a cereal bar). The subject should take his/her second dose as close as possible to 12 hours after the first dose. Then he/she will take the study medication every 12 hours for the remaining 4 days.
 - b. *Completion of subject diary.* Subjects will be instructed on completion of the electronic diary.
 - c. *Use of birth control.* Female subjects of childbearing potential, if sexually active, will be instructed to continue an acceptable method of birth control for the duration of the study and for 1 month post-treatment. Acceptable methods of birth control include a double barrier method, oral birth control pills, an IUD, or medroxyprogesterone acetate administered intramuscularly.
 - d. *Follow-up visits:* Subjects will be instructed to return to the clinic for follow-up on Day 7 and Day 22.
 - e. *Seeking emergency care or contacting the study physician or nurse:* Subjects must be informed to seek emergency medical care or contact the study physician or nurse if they develop any of the following symptoms listed below during the full 22-day study and follow-up period.

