5.10. Electronic Subject Diary

Electronic subject diaries will be completed twice daily through Day 21. The electronic diaries will capture the following information:

1. Medication intake (twice daily at time of medication intake).
2. Oral temperature (twice daily at time of medication intake). Use standard electronic oral thermometer provided by Sponsor.
3. Use of other medications taken by the subject not previously captured in the subject's medication history. Document in detail including dose in milligrams or other applicable units, time of ingestion, and the reason for use of the medication (at time of medication intake).
4. FLU-PRO Questionnaire (once daily between 7 pm and 11 pm) to characterize symptoms.
5. Activity assessment using an 11-point visual analog scale (0= unable to perform normal activity, 10= fully able to perform normal activity) (once daily between 7 pm and 11 pm).
6. Adverse experiences (once daily between 7 pm and 11 pm).

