8.3. Response Definitions

Symptom Response:	To be defined based upon a blinded review of symptom scores (pooled for all EV/RV-infected subjects without regard to treatment group assignment) that correlate to the time at which subjects report that they return to usual health (a daily global assessment question). Methodology for the correlation will be defined in the Statistical Analysis Plan. Symptom scores must be maintained at the defined level for at least 2 daily diary periods without any symptom relief medication during those 2 daily diary periods.
Time of Symptom Response:	The start of the first daily diary period in which Symptom Response is achieved and is maintained for at least 2 daily

Time to Symptom Response:	diary periods without any symptom relief medication during those 2 daily diary periods.
Ability to Perform All Normal Activities:	Time (hours) from first dose to the Time of Symptom Response.
Time of Ability to Perform All Normal Activities:	Subject reports a score of 10 on the 0-10 scale for ability to perform normal activities, which is maintained for at least 2 daily diary periods without symptom relief medication during those 2 daily diary periods
Time to Ability to Perform All Normal Activities:	The start of the first daily diary period in which the subject reports a score of 10 on the 0-10 scale for ability to perform normal activities, which is maintained for at least 2 daily diary periods without symptom relief medication during those 2 daily diary periods
Individual Symptom Response:	Time (hours) from first dose to the Time of Ability to Perform All Normal Activities
Time of Individual Symptom Response:	For each individual symptom (n=32), a score of \leq the maximum response value specified in the Symptom Response definition maintained for at least 2 daily diary periods without symptom relief medication during those 2 daily diary periods
Time to Individual Symptom Response:	The start of the first daily diary period in which the Individual Symptom Response is achieved and is maintained for at least 2 daily diary periods without symptom relief medication during those 2 daily diary periods
FLU-PRO Domain Response:	Time (hours) from first dose to Time of Individual Symptom Response

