9.6. Disallowed Medication

The following medications will not be allowed during the study: topical or systemic decongestants, nasal corticosteroids, and any prescription or non-prescription medications classified as (i) expectorants and cough preparations, (ii) analgesics and antipyretics or (iii) antihistamines (American Hospital Formulary Service (AHFS) classification). As an exception to this rule, subjects will be allowed to use acetaminophen and/or dextromethorphan as necessary for disabling symptoms .

Medications for pre-existing conditions that are not excluded (see exclusion criteria) should be continued as prescribed. The use of such medication will be recorded in the EDC system.

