**Table 4: Handling of Missing Data**

Data	Handling Convention
Adverse event onset date	
If onset date is completely missing, impute with the date of first dose.
 
If year is missing, impute with the year of enrollment.
 
If only year or if year and day are present:
 
 
• If year = year of first dose, then set month and day to the date of the first dose.
 
• If year < year of first dose, then set month and day to December 31.
 
• If year > year of first dose, then set month and day to January 1.
 
 
If month and year are present, but day is missing:
 
 
• If year = year of first dose and 
 
– If month = month of first dose, then set day to day of first dose.
 
– If month < month of first dose, then set day to the last day of the month.
 
– If month > month of first dose, then set day to the first day of the month.
 
 
 
• If year < year of first dose, then set day to the last day of the month.
 
• If year > year of first dose, then set day to the first day of the month.
 
• For all other cases, set onset date to the date of first dose.
 

Adverse event end date	If the end date is partially or completely missing, set to the last date the subject was known to be in the study.
Concomitant medications start date	
If start date is completely missing, it will not be imputed.
 
If only year or if year and day are present, set the month and day to January 1.
 
If year and month are present and day is missing, set day to the first day of the month.

Concomitant medications end date	If end date is completely missing, it will not be imputed. If only year or if year and day are present, set the month and day to December 31. If year and month are present and day is missing, set day to the last day of the month.
Concomitant medications time of dosing	If time of dosing is missing for symptom relief medication, it will be imputed as the time of the FLU-PRO Questionnaire completion for that date.

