**Table 6: Variables Used for the Primary Efficacy Analysis**

Variable	Source	Format/Notes
Date and time of first medication intake	CRF	

Variable	Source	Format/Notes
Date and time of completion for each symptom assessment record	Subject diary	
Symptom score assessment for each symptom for each diary record	Subject diary	
The ordinal symptom severity, intensity or frequency score assessment for each of the 32 symptoms will be coded to numerical values 0-4.
 
It will not be possible for any individual symptom assessment to be missing within a diary record, therefore no individual item imputation will be required.
 
In the event that the diary was not completed at a specified time point (e.g., Day 2), the missing data will not be imputed.

Date and time of symptom relief medication intake	Sponsor-provided listing	The list of symptom relief medications will be selected from the listing of all concomitant medications prior to unblinding.

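### Read literally, the eDiary item does not ask for on-study doses of a cold remedy already in the medication history, yet the primary and key secondary responses need two medication-free diary periods

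*Protocol*

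**What the plan says.** Protocol 5.10 item 3 describes the medication entry in the eDiary as "Use of other medications taken by the subject not previously captured in the subject's medication history". Entries within that scope carry dose, time of ingestion and reason, and are made when the medicine is taken. Medicines already in use are recorded by the site on Day 1 (Protocol 5.2 item 4: "Review and recording of any concomitant medications").

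Subjects who arrive already using a remedy are expected, because Protocol 3 stratifies enrollment and the primary analysis by "pre-enrollment use of symptom relief medication". Some use may continue: under Protocol 9.6, "subjects will be allowed to use acetaminophen and/or dextromethorphan as necessary for disabling symptoms".

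The endpoints depend on these records. Protocol 8.3 requires Symptom Response to hold for two diary periods "without any symptom relief medication during those 2 daily diary periods". The same condition applies to Ability to Perform All Normal Activities and to Return to Usual Health. SAP 11.2.1 builds it into both the Returned and the Responded variables from which the primary response thresholds are chosen. SAP Table 6 lists "Date and time of symptom relief medication intake" among the required variables, and Table 7 does the same for the key secondary endpoint. The source of both is a sponsor listing selected from the concomitant medications.

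**The concern.** The diary item is narrower than the endpoint it feeds. A subject with acetaminophen or dextromethorphan recorded on Day 1 can follow item 3 to the letter and leave later doses of that product out of the diary. The derivation would then see medication-free periods that were not medication-free.

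Two things are at stake. First, a subject can be scored as a responder, or scored too early, against the stated definition. This would occur mainly in the pre-enrollment-use stratum. Second, the same error enters the derivation of the Symptom Response thresholds, because each diary record is classified using the same medication condition.

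**Working it through.** The plan states no figure on this point, so the check is a comparison of texts, followed by two illustrations of the mechanism.

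**What captures an on-study dose of a baseline-listed remedy?**

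- eDiary (Protocol 5.10 item 3): outside the item's scope on a literal reading.
- Daily diary review (Protocol 5.3): checks completion and suspected errors. It cannot readily see a dose that the diary did not ask for.
- Day 2-5 calls and Day 2 and 3 visits (Protocol 5.4, 5.5): cover complications and adverse events. No concomitant-medication review is stated there.
- Day 7 and Day 22 visits (Protocol 5.6, 5.7): concomitant medications are reviewed, by recall over up to 22 - 7 = 15 days on the nominal schedule. No per-dose time is requested.
- SAP Table 4: imputes a missing time on a symptom relief dose record that exists. It has no rule for a dose never recorded, nor for mapping a start-stop range to diary periods. For stop dates it says "If end date is completely missing, it will not be imputed".
- SAP 11.2.2, last-diary rule: absence of evidence of intake is enough, so an unrecorded dose counts as no dose.

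None of these reliably supplies the dated and timed intake that Tables 6 and 7 call for.

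**One constructed subject.** SAP 11.1 defines a diary period as the 24 hours ending at the assessment, and the questionnaire is completed in the evening. Suppose the symptom thresholds are met from the Day 6 diary onward, and a baseline-listed product is taken daily, last on the afternoon of Day 9.

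- Doses logged: the Day 9 diary period contains a dose. The Day 10 and Day 11 periods are the first two that are free. Response is dated to the start of the Day 10 period, which is Day 9 evening.
- Doses not logged: the Day 6 and Day 7 periods qualify. Response is dated to Day 5 evening.
- Error: 9 - 5 = 4 days, or 4 x 24 = 96 h too early.

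**Group level, on assumed inputs.** The documents give neither the share of subjects with a remedy listed at baseline nor how many continue it. Assume 30-50% pre-enrollment users, of whom 30-60% continue the same product with none of it captured. The affected share is then 0.30 x 0.30 = 9% to 0.50 x 0.60 = 30%. Take a log-normal time to threshold (median 9 days, SD of log 0.6) and an exponential delay with mean 2 days (low case) or 4 days (high case). By simulation, the median of a single arm is dated about 4.5 h too early in the low case and about 27 h in the high case.

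Now apply the same unlogged use to both arms, with medians of 9 and 7 days. The difference between the arm medians changes by about 0 h in the low case and about 2 h in the high case. The within-arm error largely cancels when use is equal.

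**The case against.** The strongest reply is that full capture was plainly intended.

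- Protocol 7.1 says subjects record concomitant medications in the app, without exception.
- SAP 8.2 says subjects are instructed on recording them, and the Schedule of Assessments repeats instruction at baseline, Days 2-5 and Day 7.
- SAP 11.1 defines symptom relief medication as anything the subject reports taking for a cold symptom during the study. SAP Table 9 expects a reason for each such medicine.
- Item 3 itself can be read so that the limiting phrase applies to the use rather than the product. An on-study dose is then always new. Medication history is not defined, and the eDiary prompt is not in the documents.
- The start-stop dates in SAP Table 5 belong to a report listing. The derivation uses a separate intake listing, and the Table 4 rule for missing dosing times presupposes dose-level records.
- Protocol 9.6 limits which remedies may be continued, so fewer subjects are exposed than the baseline list suggests.

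Most of this stands as evidence of intent, and it narrows the exposure. It does not cure the conflict. An intake listing can hold only what was recorded, and an instruction on which the primary endpoint depends should not be open to both readings.

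A reader might infer more: that the treatment comparison is biased, for example because placebo subjects medicate longer, or that 96 h or 27 h is large against the planned 48 h reduction in the median. The documents do not support either inference. The 96 h belongs to one invented subject and the 27 h to one arm's median, whereas the 48 h is a difference between arms. Which arm would continue a remedy longer is not known.

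**Conclusion.** The point holds as a conflict between the diary instruction and the endpoint definitions. Followed literally, item 3 leaves some on-study doses unlogged and can date a response too early, mainly among pre-enrollment users. The size cannot be estimated from the documents, and the group-level figures above only illustrate assumed rates.

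Subjects and staff are blinded, and both randomization and the primary analysis are stratified on pre-enrollment use. The main expected effect is therefore misclassification of response. No direction of bias in the treatment comparison is established. The conclusion rests on the literal reading of item 3, and a differently worded eDiary prompt could already have closed the gap. The point merits correction because the primary endpoint depends on these records and the correction is cheap.

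**What to change.** Reword Protocol 5.10 item 3 and the eDiary prompt. Every intake of any medicine taken for a cold symptom, from first dose through Day 21, should be recorded with its time and reason, whether or not the medicine is in the medication history.

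If data collection is over, which the planned end in April 2019 and the SAP version of July 2019 suggest, add a sensitivity analysis to the SAP before unblinding. It should treat every day within the recorded start-stop range of a baseline-listed symptom relief medicine as a medication day. Records without a stop date should be handled both ways: once as use continuing to the last diary, and once as no use beyond what is recorded.

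This should not replace the primary derivation. Carrying use forward to the last diary could turn a subject who recovered early after occasional use into a censored non-responder.

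The cost is slightly more diary entry for some subjects and one extra analysis.

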5.11. Plan for Laboratory Safety Tests

A central laboratory will be used for laboratory safety testing. Blood tests will include hemoglobin, hematocrit, complete blood count (total and differential), platelet count, random blood sugar, total cholesterol, HDL, LDL, triglycerides, albumin, AST, ALT, GGT, alkaline phosphatase, bilirubin (total/direct), BUN, creatinine, sodium, potassium, chloride. Routine urinalysis will include glucose, protein, and blood.

5.12. Plan for Virology Testing and Monitoring Resistance

Virology testing of nasopharyngeal swab samples will be conducted as described on the following pages.

Table 10: Virology testing of nasopharyngeal swabs

	Day 1	Day 2	Day 3	Day 7	Day 22
RT-PCR by ePlex RPP for Virus Detection	X	X ¹	X ²	X ³	X ⁴
Sequencing for EV/RV Typing	X ⁵				
Quantitative PCR	X ⁶	X ⁶	X ⁶	X ⁷	
Culture & Susceptibility Testing for Resistance Monitoring	X ⁸			X ⁸	X ⁸
Nucleotide Sequencing	X ⁹			X ⁹	X ⁹

¹ If Day 1 sample is negative for EV/RV by RT-PCR² If Day 2 sample is negative for EV/RV by RT-PCR³ Only if one of Day 1, 2, or 3 samples is positive for EV/RV for RT-PCR⁴ If Day 7 sample is positive for EV/RV by RT-PCR⁵ Only the earliest sample positive for EV/RV by RT-PCR of those collected at Days 1, 2, and 3 will be sequenced for EV/RV type⁶ A sample will only be subjected to quantitative PCR if one of the Day 1, 2, or 3 samples is positive for EV/RV by RT-PCR⁷ The Day 7 sample will be subjected to quantitative PCR only if one of the Day 1, 2, or 3 samples AND the Day 7 sample is positive for EV/RV by RT-PCR⁸ If the Day 1 and Day 7 or Day 1, 7, and 22 samples are positive for EV/RV by RT-PCR each sample will be cultured and tested for susceptibility to tizoxanide. Results observed for the Day 7 and Day 22 samples will be compared to the results observed for the Day 1 sample.⁹ Sample pairs exhibiting resistance to tizoxanide will be subjected to sequencing.

1. Collection of samples:

Two nasopharyngeal swabs will be collected from each subject at Baseline (Day 1) and Days 2, 3, 7 and 22.

2. Testing of biological samples:

a. Each Baseline sample will be subjected to RT-PCR using the ePlex® Respiratory Pathogen Panel (GenMark, Carlsbad, CA) to detect influenza A (non-specific as to subtype); influenza A H1, H1N1 (2009), H3 subtypes; influenza B; respiratory syncytial virus A and B (RSV); parainfluenza 1, 2, 3 and 4; human metapneumovirus (hMPV); adenovirus; human EV/RV; coronavirus NL63, HKU1, 229E and OC43; human bocavirus; *Chlamydophila pneumoniae*; *Legionella pneumophila*; and *Mycoplasma pneumoniae*.

b. If a subject's Baseline sample is negative for EV/RV by RT-PCR, his/her Day 2 and Day 3 samples will be subjected to RT-PCR using the ePlex® Respiratory Pathogen Panel to detect respiratory pathogens.

c. If the Baseline sample or the Day 2 or Day 3 sample is positive for EV/RV, the earliest positive sample will be sequenced to determine virus type and each of the Baseline, Day 2 and Day 3 samples will be subjected to quantitative PCR testing to quantify viral shedding.

d. All Day 7 samples will be subjected to RT-PCR using the ePlex® Respiratory Pathogen Panel. Day 7 samples positive for EV/RV will also be subjected to

quantitative PCR testing to quantify viral shedding if one of the Day 1, 2, or 3 samples was also positive for EV/RV.

- e. Day 22 samples will be subjected to RT-PCR using the ePlex® Respiratory Pathogen Panel only if the sample collected at the preceding time point (Day 7) had detectable EV/RV.
3. Drug susceptibility testing:
 - a. If any Day 7 or Day 22 sample is positive for EV/RV by RT-PCR and one of the Day 1, 2, or 3 samples was also positive for EV/RV, the virus will be isolated (if possible) and tested for susceptibility to tizoxanide (TCID₅₀).
 - b. The Baseline isolate for subjects with virus cultured at Day 7 or 22 will also be tested for susceptibility to tizoxanide, and the results will be compared to the results observed for the Day 7 or 22 isolate.
4. Nucleotide sequencing:
 - a. All Day 7 or 22 samples with resistance ($IC_{50} \geq 10x IC_{50}$ at Baseline) to tizoxanide will be subjected to sequencing. The corresponding Baseline sample will also be subjected to nucleotide sequencing. Initial genotypic assessments of resistance to tizoxanide will focus on isolates displaying the largest shifts in susceptibility.
 - b. Sequencing data for Day 7 or 22 isolates with resistance to tizoxanide will be compared to sequence data for the Baseline sample to identify mutations that may confer resistance.
5. Storage of samples: All samples collected during the study will be stored for at least 2 years for potential future testing.
6. Clinical Virology Laboratory for diagnostic testing:
[REDACTED]

7. Clinical virology laboratory for sequencing, quantification of viral shedding, and susceptibility testing:
[REDACTED]

